#### **6.8.3      Supplementary FDA Recommended Efficacy Analyses**

Supplementary analysis will be conducted utilizing the Kaplan-Meier technique to estimate the proportion of patients who achieve and maintain castrate T levels (<0.5 ng/mL or 1.73 nmol/L) from Day 28 through the end of the treatment period using the ITT population.

Treatment failure [non-castrate serum T levels ( $\geq 0.5$  ng/mL or 1.73 nmol/L) with central lab] will be defined as the analysis event.

The following patients will be considered as experiencing an event

1. Patients who did not achieve castrate serum T levels (<0.5 ng/mL or 1.73 nmol/L) by Day 28. Day 28 will be considered as the day of event.
2. Patients who successfully achieve a castrate serum T level by Day 28 but fail to maintain it throughout the treatment period. Day of failure (day of sampling) will be considered as the day of event.

---

Document:

C:\ProgramData\activePDF\Temp\DocConverter\API\Input\\$651f4dc0b253\$FE3041C5883446E892B20AB6D3F0E1BD.docx

Author: [name]

Version and Date: Version 1.0, 21 Apr 2023

Page 62 of 66

The following patients will not be considered as having experienced an event:

[figure not shown]
- 1 Patients who achieve and maintain castrate serum T levels with central lab from Day 28 through the end of the treatment period.
- 2 Patients who leave the trial for reasons other than a non-castrate serum T levels.

Censoring and handling of missing data rules will be used for this analysis:

[figure not shown]
- 1 Patients who achieve and maintain castrate serum T levels with central lab from Day 28 through the end of the treatment period will be censored at their last serum T level assessment.
- 2 Patients who leave the trial for reasons other than a non-castrate serum T level will be censored at their last serum T level assessment.
- 3 Patients with one or more consecutive missing serum T levels and a non-castrate serum T level after the missing time point(s) will be considered to have had an event (treatment failure) at the first missing time point. For example: if the subject's data is missing for Days 28 and 35 and having a non - castrate T levels ( $\geq 0.5$  ng/mL) on Day 42 we should consider that the subjects had an event on day 28.

- 4 Patients with castrate serum T levels immediately before and after a single missing serum T level will not be considered to have had an event (treatment failure) at the missing time point. For example: if the subjects have castrate T levels ( $<0.5$  ng/mL) for Days 28 and 42 but data on day 35 is missing will not be considered to have had an event on day 35.

- 5 Patients with two or more consecutive missing serum T levels and castrate serum T levels immediately before and after the missing time points will be censored at their last T level before the missing data. For example: if the subjects have missing castrate T levels ( $<0.5$  ng/mL) for Days 35, 42 but have data on day 28 and 84 the data on Day 28 will be censored.

Time to event will be calculated as: **(date of event - date of Day 28) + 1**.

The presentation of the results will include the median by Kaplan-Meier function, 95% CI for Kaplan-Meier median and the Kaplan-Meier survival curve. The proportion of participants achieving castration level with serum T  $<0.5$  ng/mL or 1.73 nmol/L across the treatment period from Day 28

Document:

C:\ProgramData\activePDF\Temp\DocConverter\API\Input\\$651f4dc0b253\$FE3041C5883446E892B20AB6D3F0E1BD.docx

Author: [name]

Version and Date: Version 1.0, 21 Apr 2023

Page 63 of 66

to Day 168, along with Clopper-Pearson CI of the proportion will be presented for both ITT and PP Population at each assessment point.

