In the case of advanced prostate cancer, suppression of T to castration levels (<0.5 ng/mL) was achieved within 3 days in the majority of the participants and this was maintained for 4 to 8 weeks. Some participants experienced transient castration breakthrough, where T concentrations temporarily increased to ≥0.5 ng/mL. Teverelix TFA was also shown to rapidly reduce and normalise PSA levels.

Pharmacokinetic (PK) and pharmacodynamic (PD) data from 2 studies indicate that the SC route of administration for teverelix TFA produces a more sustained suppression of T levels than the IM route. No safety concerns were identified in any of the conducted clinical studies. The most frequently reported adverse events (AEs) were mild ISRs and reversible symptoms characteristic of T and oestrogen deprivation, such as hot flushes, decrease in libido and potency, and reduction in testis size. No serious adverse events (SAEs), considered to be at least possibly related to the administration of teverelix TFA, have been reported [11].

ANT-1111-02, Teverelix TFA in Prostate Cancer FINAL Version 5.0, 31 May 2022 Page 30 of 84

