In case a start date for an AE is missing or incomplete, so that it is not possible to evaluate if it has occurred pre- or post-treatment, this AE will be classified conservatively as treatment-emergent. More information on missing data imputation will be described in the SAP.

8.1.7 **Multicentre Study**

This study will be performed as a multicentre study. Count and proportion of participants achieving castration level within the first 28 days, and participants maintaining castration over the 168-day treatment period will be stratified by site. No other risks are expected.

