8.1.10 Interim Analysis

After completion of Stage 1, i.e. after all participants have completed the visit at Day 28 and their T concentration levels are available, an analysis of the primary efficacy parameter will be performed analysing the number and proportion of participants reaching castration level by Day 28 with the loading dose of teverelix TFA.

The study will proceed during the analysis and all other efficacy, safety and demographic parameters will be evaluated at the end of the study (full analysis, Stage 2).

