#### **4.1.1 Primary Efficacy Measure**

The primary efficacy measure is the proportion of subjects achieving castration with central lab serum T <0.5 ng/mL or 1.73 nmol/L at Day 28. The denominator is the number of subjects who have a non-missing central lab T record at Day 28 in the relevant population.

---

Document:

C:\ProgramData\activePDF\Temp\DocConverter\API\Input\\$651f4dc0b253\$FE3041C5883446E892B20AB6D3F0E1BD.docx

Author: [name]

Version and Date: Version 1.0, 21 Apr 2023

Page 29 of 66

The primary parameter analysis will be performed on the PP analysis set. In addition, a sensitivity analysis will be performed on the ITT analysis set.

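### SAP 6.8.3 counts castration from Day 28 but sorts events by castration reached by Day 28, so a man who escapes before Day 28 has no single event status or date

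*SAP*

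**What the plan says.** SAP 6.8.3 (Supplementary FDA Recommended Efficacy Analyses) estimates the proportion of men meeting this description: "achieve and maintain castrate T levels (<0.5 ng/mL or 1.73 nmol/L) from Day 28 through the end of the treatment period using the ITT population". The rules that carry this out are:

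- Event rule 1: "Patients who did not achieve castrate serum T levels (<0.5 ng/mL or 1.73 nmol/L) by Day 28". The event is dated Day 28.
- Event rule 2: "Patients who successfully achieve a castrate serum T level by Day 28 but fail to maintain it throughout the treatment period". On its date: "Day of failure (day of sampling) will be considered as the day of event".
- Non-event rule 1 and censoring rule 1: men castrate by central laboratory from Day 28 to the end of treatment are not events.
- Time to event: event date minus Day 28 date, plus 1.

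The first sensitivity analysis to 6.8.3 repeats both event rules.

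The SAP uses the term treatment period in two ways. Section 2.2.1 lists Stage 1 (Day 0 to Day 28) under it. Sections 4.1.2 and 6.8.2, and the results paragraph of 6.8.3 itself, attach it to Day 28 to Day 168.

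The primary measure in SAP 4.1.1 is the "proportion of subjects achieving castration with central lab serum T <0.5 ng/mL or 1.73 nmol/L at Day 28". The protocol words related summaries more loosely: "number and proportion of participants reaching castration level by Day 28" in 8.1.10 and "Count and proportion of participants achieving castration level within the first 28 days" in 8.1.7.

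**The concern.** Protocol 1.2.2 reports castration within 3 days in most earlier participants with advanced prostate cancer. Few men will therefore meet event rule 1, and most will be governed by rule 2. The same section adds: "Some participants experienced transient castration breakthrough, where T concentrations temporarily increased to ≥0.5 ng/mL". Central T is drawn at 24, 48 and 72 hours and on Days 4, 7, 10, 12, 14 and 21 (SAP Table 18), so an escape before Day 28 can be seen. A man whose local T at Day 21 lies between 0.5 and 2 ng/mL stays in the study, and if he gives a central Day 28 sample he enters the ITT set.

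For such a man the rules do not give one answer. The programmer would have to drop, floor or recode his record, and the SAP does not say which. The analysis was added after discussion with the FDA (SAP 7.1), so its event definition should not be settled at the programming stage.

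**Working it through.** The plan gives no numerical figure for this analysis, so there is none to reproduce. The sample size in protocol 8.1.12 rests on the primary endpoint and does not depend on it.

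**Step 1: times under the written formula.** Time = (event date − Day 28 date) + 1. Visit windows are ±1 day for Days 14 and 21 and ±3 days for Day 28 (SAP Table 19).

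- Sample at Day 21: (21 − 28) + 1 = −6. Over the windows, (20 − 31) + 1 = −10 to (22 − 25) + 1 = −2.
- Sample at Day 14: (14 − 28) + 1 = −13. Over the windows, (13 − 31) + 1 = −17 to (15 − 25) + 1 = −9.
- Sample at Day 7: (7 − 28) + 1 = −20.
- Sample at Day 28: (28 − 28) + 1 = 1.

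A failure dated at any scheduled visit before Day 28 gets a negative time, which a curve starting at Day 28 cannot use.

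**Step 2: two men under two readings.** Man A is castrate on Day 3 and at 0.7 ng/mL on Days 21 and 28. Man B is castrate on Day 7, non-castrate on Day 14, and castrate from Day 28 to Day 168. Neither meets event rule 1, because both reached castration before Day 28.

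| | Treatment period from Day 0 (SAP 2.2.1) | Treatment period from Day 28 (SAP 4.1.2, 6.8.2) |
|---|---|---|
| Man A | Event under rule 2; −6 if the failure is dated at Day 21 | Event under rule 2 at time 1 |
| Man B | Event under rule 2 at −13, and a non-event under non-event rule 1 | Non-event |

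**Step 3: what the choice can do to the estimate.** Assumptions, none of them from the documents: 50 men, k early escapers still non-castrate at Day 28, 2 later failures, no other censoring.

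| k | Escapers count as failures: (50 − k − 2)/50 | Negative-time records dropped: (50 − k − 2)/(50 − k) |
|---|---|---|
| 1 | 47/50 = 94% | 47/49 = 95.9% |
| 3 | 45/50 = 90% | 45/47 = 95.7% |
| 5 | 43/50 = 86% | 43/45 = 95.6% |

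If the k men have instead recovered by Day 28, like Man B, counting them as non-events gives (50 − 2)/50 = 96%. Counting them as events gives the 94% to 86% column, so for these men the literal rule works against the drug.

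**The case against.** The best defence is that 6.8.3 can be read sensibly as it stands. The estimand, non-event rule 1 and the first censoring rule all start at Day 28. The worked missing-data examples use Day 28 or later, the formula gives Day 28 a time of 1, and the results paragraph speaks of Day 28 to Day 168. On that reading Man A fails at time 1, Man B does not fail, and no time is negative. The section also reports the castrate proportion with a Clopper-Pearson interval at each assessment point, so failures would stay visible.

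Most of this stands, and it makes negative times conditional on the reading. It does not remove the conflict. Event rules 1 and 2 still sort men by what happened before Day 28, SAP 2.2.1 still places Stage 1 inside the treatment period, and no Day 28 floor is written.

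Four stronger readings are tempting but not supported:

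- That the SAP dates failure at the first non-castrate sample. It names the day of failure and does not say first.
- That the curve must start at 100% when the Day 28 result is 90%. This needs the Day 0 reading, every Day 28 failure to have overstepped earlier, and those records to be discarded. The SAP does not say they are discarded, and the breakthrough sentence in protocol 1.2.2 gives no timing.
- That the error always favours the drug. Man B, kept as an event, counts against it.
- That the primary result is inflated because protocol 8.1, 8.1.7, 8.1.10 and the synopsis say by or within 28 days. The primary endpoint is at Day 28 in protocol 8.1.3 and SAP 4.1.1 and 6.8.1. The 8.1.7 summary is a by-site table that does not name the primary endpoint, and 8.1.10 attaches no decision to its analysis and lets the study proceed meanwhile.

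**Conclusion.** The concern holds as a conflict between stated rules in one supplementary analysis and its first sensitivity analysis. The estimand counts castration from Day 28, while the event rules classify men by castration reached by Day 28 and set no earliest event date. Two defensible readings can give different curves.

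The documents do not fix the size. Under the assumptions in step 3, the gap between counting the escapers as failures and losing their negative-time records runs from about 2 points with one escaper to about 10 points with five. Its direction depends on how such records are handled and on whether the men have recovered by Day 28. Only men with a central Day 28 sample are affected, because the ITT set requires one. The primary analysis is not touched. The rules should be corrected, but this is not a fault in the trial's main result.

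**What to change.** Replace the two event rules in SAP 6.8.3, and use the same wording in its first sensitivity analysis:

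1. Central T ≥0.5 ng/mL at the Day 28 visit is an event at Day 28, with time 1.
2. Central T <0.5 ng/mL at the Day 28 visit, followed by a first T ≥0.5 ng/mL at a later scheduled visit up to Day 168, is an event on that sampling day.

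State that samples before the Day 28 visit do not count, including in the missing-data rules, and that the Day 28 date in the formula is the actual date of the Day 28 sample. The smallest possible time is then 1, and nominal times are (35 − 28) + 1 = 8 at Day 35 and (168 − 28) + 1 = 141 at Day 168. Man A is an event at time 1 and Man B a non-event on any reading.

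The cost is a few sentences in the SAP and no change to data collection or sample size. SAP 7.2 bars changes to the SAP after database lock, so the edit must come before it. Changing the by and within wording to at Day 28 in protocol 8.1, 8.1.7, 8.1.10 and the synopsis is editorial. Protocol 10.2 requires a formal amendment for any protocol change, so this can wait for the next one.

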After Stage 1, participants in Group 1 will receive a maintenance dose, which will consist of a single 120 mg SC injection administered every 42 days.

[figure not shown]
If the serum T value (measured by the local laboratory) at the Day 35 visit is >2 ng/mL, the participant will be withdrawn from the study.

If 3 or more participants have a total T (local laboratory) value of >2 ng/mL at Day 21 or at any subsequent study visit, the dosing regimen will have failed to meet its 90% efficacy target and, if applicable, further enrolment into Group 1 will cease.

If treatment of Group 1 has been terminated early due to a low therapeutic response rate, recruitment of participants into Group 2 will start.

After Stage 1, participants in Group 2 will receive a maintenance dose, which will consist of a single 180 mg SC injection administered every 42 days.

Page 39 of 84

If the serum T value (measured by the local laboratory) at the Day 21 visit is >2 ng/mL, the participant will be withdrawn from the study.

Participants will have their serum T measured by the local laboratory 1 week prior to each maintenance dose during Stage 2 of the study. If, at any point the local laboratory serum T result is >2 ng/mL the participant will be withdrawn from the study. Local laboratory serum T values ≤ 2 ng/mL allow the subjects to continue in the study.

Table 3 describes the decision-making process for doses participants will receive based on the results of the locally analysed T level from 7 days prior to the scheduled dosing visit.

Table 3: Decision-making in Relation to Serum Testosterone Levels

[T] (ng/mL)	Action Taken	Dose Administered
≤2	Continue in Stage 2	Group 1: Maintenance dose 120 mg
		SC teverelix TFA
		Group 2: Maintenance dose 180 mg
		SC teverelix TFA
>2	Withdrawal from study, safety	None
	follow-up visit	

SC=subcutaneous; T=testosterone; TFA=Trifluoroacetate

Depending on the level of T prior to dosing, a decision will be made regarding whether to continue the participant in the study, request a re-test 7 days prior to the next scheduled dosing visit, or initiate early study withdrawal. If T levels are ≥ 2 ng/mL, the participant will be withdrawn from the study.

In the event that a participant of Group 1 will be continued during Stage 2, each dose will be administered according to Table 4: Testosterone Testing in Groups 1 and 2 every 6 weeks.

Table 4: Testosterone Testing in Groups 1 and 2

Local [T] Testing	Teverelix TFA Dose

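### SAP 6.8.3 states conflicting rules for missed samples and for men who leave, with no order of precedence, so one man's event date or status can depend on which rule is applied

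*SAP*

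**What the plan says.** SAP 6.8.3 defines the event as non-castrate central T, 0.5 ng/mL or more. It then gives three lists: who has an event, who does not, and how to censor and handle missing values.

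- **Event rule 2:** "Patients who successfully achieve a castrate serum T level by Day 28 but fail to maintain it throughout the treatment period" have an event, dated on the day of sampling.
- **Non-event item 2:** "Patients who leave the trial for reasons other than a non-castrate serum T levels" have no event. Censoring rule 2 censors them at their last T.
- **Rule 3** begins: "Patients with one or more consecutive missing serum T levels and a non-castrate serum T level after the missing time point(s) will be considered". It dates the failure at the earliest visit in the gap. In the example, Days 28 and 35 are missing and Day 42 is non-castrate: "we should consider that the subjects had an event on day 28".
- **Rule 4** reads: "Patients with castrate serum T levels immediately before and after a single missing serum T level will not be considered to have had an event". That is, no failure is assigned to the missed visit.
- **Rule 5** covers gaps of two or more visits: men with "castrate serum T levels immediately before and after the missing time points will be censored at their last T level before the missing data".

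The section does not say which rule prevails when two apply.

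Withdrawal for lack of suppression uses a different laboratory and a different cut-off. Protocol 5.5 says: "If, at any point the local laboratory serum T result is >2 ng/mL the participant will be withdrawn from the study". Men at or below 2 ng/mL continue.

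**The concern.** Two sets of rules overlap.

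1. **Gaps.** Rule 3 lacks the word that rules 4 and 5 both carry, requiring the neighbouring value to be adjacent. As worded, a non-castrate value at any later visit triggers rule 3, even when castrate values enclose the gap.
2. **Leavers.** Neither leaver statement requires that no failure has yet been observed. A man with central T between 0.5 and 2 ng/mL has had an event but stays in the trial. If he later leaves for an unrelated reason, he is on both the event list and the no-event list.

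The first overlap can move an event date or, through rule 5, replace a later observed failure with censoring. The second can remove a failure that was seen. This is the FDA-recommended estimate of maintained castration, and its result should not depend on how a programmer resolves the wording.

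**Working it through.** The plan states no figure for this point, so the check is to apply the rules as written.

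**Inputs.** Central T is scheduled at Days 28, 35, 42, 84, 126 and 168 (SAP Table 7). The ITT set requires a Day 28 central value (SAP 3.4). C is castrate, N non-castrate, M missing.

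**The SAP's own examples.** The coded rules return all three: M, M, N gives an event at Day 28; C, M, C gives no event at Day 35; C, M, M, C gives censoring at Day 28.

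**Patterns that fall under more than one rule**

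| Pattern | Rule 3, any later value | Rule 4 or 5 | Event rule 2 |
|---|---|---|---|
| C D28, M D35, C D42, N D84 | event D35 | rule 4: no event at D35 | event D84 |
| C D28, M D35, M D42, C D84, N D126 | event D35 | rule 5: censored D28 | event D126 |

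In the first row the man fails on either reading and only the date moves. In the second, rule 5 removes the failure.

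**How many patterns.** With Day 28 castrate there are 3^5 = 243 patterns over the other five visits. On the any-later reading, rule 3 conflicts with rule 4 in 26 and with rule 5 in 7. On the immediately-next reading both counts are 0. In 7 patterns rule 5 still censors a man whose later sample is non-castrate. These are counts of patterns, not probabilities.

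**Size of the gap conflict (assumed data).** Take 50 men: two events at Day 28, three at Day 84, one man with the second pattern above, and 44 castrate throughout.

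- He is an event, at Day 35 or Day 126: Day 168 estimate = 44/50 = 88.0%.
- He is censored at Day 28: (48/50) × (44/47) = 89.9%.
- Day 42 estimate: 47/50 = 94% if he fails at Day 35, otherwise 48/50 = 96%.

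The rule 5 route should be rare. Take five failures, three at Day 84 and two at Day 126, and independent loss of each sample with probability q. Only the Day 126 failures can have a rule 5 gap before them (Days 35 and 42 missing, Days 84 and 126 observed). The expected number is 2q²(1−q)², which is 0.0008, 0.0045 and 0.016 men for q = 2%, 5% and 10%. These values of q are assumptions.

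**Size of the leaver conflict (assumed data).** Take 50 men with failures at Day 84 (three) and Day 126 (two).

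- All five counted: (47/50) × (45/47) = 90.0%.
- Two Day 84 failures recoded as censored at Day 126: (49/50) × (47/49) = 94.0%.

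**The case against.** The strongest reply is that the rules have a coherent reading. Rules 3 to 5 sort gaps by what lies on either side, and rule 3's only example uses the very next value. On that reading rules 3, 4 and 5 do not overlap. This largely stands, although the example has Day 28 missing, which cannot occur in the ITT set, and the wording of rule 3 is still broader than its example.

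Rule 5 can also be read as a deliberate end of follow-up at a long gap. That is a legitimate convention, but the SAP should say so, because event rule 2 still counts the later failure.

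On leavers, ordinary Kaplan-Meier practice takes the first event, so a later departure could not censor a man who had already failed. That is the sensible reading, but it is unwritten. It cannot be presumed in this SAP: item 7 of 6.8.2, on time to first overstep, lists men who fail to maintain castration as censored on the day of failure, although overstep is the event there.

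The first sensitivity analysis counts all leavers, and all men with two or more consecutive missing values, as events. This limits both routes by which a failure could be lost. It does not correct the main supplementary estimate or settle the single-gap date.

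A reader might infer that rule 3 reaches into Stage 3, so that T recovery off drug turns any lost sample into a failure. The documents do not support this. SAP 6.8.3 confines the analysis to the treatment period from Day 28 to Day 168, the protocol synopsis ends treatment with the Day 168 dose, and recovery after that dose is a separate endpoint (6.8.2, item 8). Nor do the documents show that a reading would be chosen to suit the results.

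**Conclusion.** The conflict is real on the words of SAP 6.8.3, but minor. The wording of rule 3 is broader than its example and clashes with rules 4 and 5. Against rule 4, only the event date is at stake. The leaver statements do not depend on how rule 3 is read and, taken literally, remove observed failures in men with T of 0.5 to 2 ng/mL who later leave for another reason.

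The 90.0% to 94.0% shift is an illustration. It assumes that two of five failures later leave for unrelated reasons and that the leaver rule is applied over the event rule. The documents give no rate for either. A reader might infer that failures will in fact be erased. The documents support only that the written rules permit it. The primary Day 28 endpoint is unaffected.

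**What to change.** Amend SAP 6.8.3 as follows:

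1. In rule 3, require *a non-castrate serum T level immediately after the missing time point(s), at or before Day 168*.
2. State the precedence: the first observed central T of 0.5 ng/mL or more from Day 28 to Day 168 is the event, and no later missing visit or departure removes it.
3. Limit non-event item 2 and censoring rule 2 to men castrate at every available assessment from Day 28 until they leave.
4. If rule 5 is meant to end follow-up at the gap, keep it and say in one sentence that later values are then not used.

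The cost is a few sentences in the SAP and the matching program logic. No new data are needed.
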